#### **6.4.2.2 Analysis of Secondary Efficacy Endpoint: Disease Control Rate per iRECIST (iDCR)**

iDCR for each group will be calculated and its 95% confidence interval will be constructed by Clopper-Pearson method by investigator assessment for the endpoints of:

- iDCR with confirmed response by investigator assessment
- iDCR with unconfirmed response by investigator assessment

#### **6.4.2.3 Analysis of Secondary Efficacy Endpoint: Disease Control Rate per RECIST v1.1 (DCR)**

DCR for each group will be calculated and its 95% confidence interval will be constructed by Clopper-Pearson method by investigator assessment for the endpoints of:

- DCR with confirmed response by investigator assessment
- DCR with unconfirmed response by investigator assessment

#### **6.4.2.4 Analysis of Secondary Efficacy Endpoint: Overall Survival (OS)**

OS data will be listed.

#### **6.4.2.5 Analysis of Secondary Efficacy Endpoint: Progression-Free Survival per iRECIST (iPFS)**

iPFS data will be listed.

#### **6.4.2.6 Analysis of Secondary Efficacy Endpoint: Progression-Free Survival per RECIST v1.1 (PFS)**

PFS data will be listed.

#### **6.4.2.7 Analysis of Secondary Efficacy Endpoint: Duration of Response per iRECIST (iDOR)**

iDOR data will be listed.

#### **6.4.2.8 Analysis of Secondary Efficacy Endpoint: Duration of Response per RECIST v1.1 (DOR)**

DOR data will be listed.

### **6.5 Analysis of Safety**

Safety analyses will be conducted using the SAF. Safety analyses will be summarized by dose level, phase, and overall.

#### **6.5.1 Dose Limiting Toxicities**

Dose evaluation and dose escalation stopping rules based on the BOPIN design with target DLT rate of 0.30 and optimal interval of (0.236, 0.359) are as follows:

Action	Number of Participants Treated at Current Dose Level						
	3	4	5	6	7	8	9
Escalate dose if number of participants with DLT $\leq$	0	0	1	1	1	1	2
Stay at current dose level if number of participants with DLT =	1	1	NA	2	2	2	3
De-escalate if number of participants with DLT =	2	2	2 or 3	3	3 or 4	3 or 4	4
Stop if number of participants with DLT $\geq$	3	3	4	4	5	5	5

DLT: dose limiting toxicity

### **6.5.2 Adverse Events**

For the purpose of safety assessments in this study, events recorded during the pre-investigational period will be classified as Baseline Signs and Symptoms. All AEs recorded on treatment including within 30 days from the last study treatment and SAEs on treatment including within 90 days of the last study treatment will be summarized.

Summaries and listings of SAEs and Serious TEAEs include SAEs upgraded by the sponsor based on review of the Sponsor's list of Always Serious terms if any upgrade was done.

The coding dictionary for this study will be Medical Dictionary for Regulatory Activities (MedDRA). It will be used to summarize AEs by SOC and PT. AEs will be graded using National Cancer Institute's Common Terminology Criteria for AEs (NCI-CTCAE).

An overview table will include the following details by dose level, phase, and overall:

- Number and percentage of participants with TEAEs
- Number and percentage of participants with IP-related TEAEs
- Number and percentage of participants with TEAE leading to death
- Number and percentage of participants with IP-related TEAE leading to death
- Number and percentage of participants with serious TEAEs and Astellas upgraded serious TEAE
- Number and percentage of participants with serious IP-related TEAEs and Astellas upgraded serious IP-related TEAE
- Number and percentage of participants with TEAEs leading to permanent discontinuation of study IP
- Number and percentage of participants with IP-related TEAEs leading to permanent discontinuation of study IP
- Number and percentage of deaths

The number and percentage of participants with TEAEs, as classified by SOC and PT will be summarized by dose level, phase, and overall. Summaries will be provided for:

- DLTs within the DLT observation period
- All DLTs
- TEAEs
- IP-related TEAEs
- Serious TEAEs and Astellas upgraded serious TEAE
- IP-related serious TEAEs and IP-related Astellas upgraded serious TEAE
- TEAEs leading to permanent discontinuation of study IP
- IP-related TEAEs leading to permanent discontinuation of study IP
- TEAEs excluding serious adverse events that equal to or exceed a threshold of 10% in any dose level
- Common TEAEs that equal to or exceed a threshold of 10% in any dose level
- TEAEs leading to death
- IP-related TEAE leading to death
- CTCAE Grade 3 or higher TEAEs
- IP-related CTCAE Grade 3 or higher TEAEs

In addition, the number and percentage of participants with TEAEs, and TEAEs leading to death, as classified by PT only, will be summarized by dose level, phase, and overall.

AE summary tables will include participant counts as opposed to AE counts. If a participant experiences more than one episode of a particular AE, that participant will be counted only once for that event. If a participant has more than one AE that code to the same preferred term, the participant will be counted only once for that preferred term. Similarly, if a participant has more than one AE within a body system, the participant will be counted only once in that body system.

The number and percentage of participants with TEAEs, as classified by SOC and PT will also be summarized by NCI-CTCAE severity grade (including < Grade 3 and  $\geq$  Grade 3). The same summary will be done for IP-Related TEAEs. In the participant count, if a participant has multiple TEAEs with the same SOC or PT, but with differing severity grade or relationship, then the participant will be counted only once with the worst severity grade and highest degree of relationship, however, if any of the severity grade or relationship values are missing then the participant will be counted only once with missing severity grade or relationship.

The list of adverse events to be summarized may change during the course of the study due to ongoing pharmacovigilance.

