7.3 Adverse Events and Other Safety Aspects

The definitions of an AE or SAE can be found in [Sections [10.3.1](#) and [10.3.2](#)], respectively. AEs will be reported by the participant (or, when appropriate, by a caregiver, surrogate, or the participant's legally authorized representative).

The investigator and any qualified designees are responsible for detecting, documenting and recording events that meet the definition of an AE or SAE and remain responsible for following up AEs that are serious, considered related to the study IP and other procedures, or that caused the participant to discontinue the IP and other procedures and/or study [see Section [10.3](#) Appendix 3: Adverse Events: Definitions and Procedures for Recording, Evaluating, Follow-up and Reporting].

The method of recording, evaluating, and assessing causality of AE and SAE and the procedures for completing and transmitting SAE reports are provided in [Section [10.3](#) Appendix 3: Adverse Events: Definitions and Procedures for Recording, Evaluating, Follow-up and Reporting].

7.3.1 Time Period and Frequency for Collecting Adverse Event and Serious Adverse Event Information

All SAEs will be collected from the signing of the ICF until the follow-up visit at the time points specified in the schedule of assessments [[Table 1](#) through [Table 3](#)] and reported on the eCRF.

All AEs will be collected from the signing of the ICF until the follow-up visit at the time points specified in the schedule of assessments [[Table 1](#) through [Table 3](#)] and reported on the eCRF.

If the NCI-CTCAE grade/grade of an SAE/AE changes, the event should be relisted on the eCRF with the new NCI-CTCAE grade/grade and new onset date.

If the NCI-CTCAE grade/grade of an SAE/AE decreases, the SAE/AE should be relisted on the eCRF with the new NCI-CTCAE grade/grade and new onset date. The exception is ongoing pre-dose events that continue post-dose and improve post-dose. Such events should not be re-listed.

If the NCI-CTCAE grade/grade of an SAE reduces, the details of the AE should be provided on the SAE worksheet for the medical assessor to be able to assess the course of the event.

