10.3.4 Assessment of Severity

AEs, including abnormal clinical laboratory values, will be graded using the NCI-CTCAE guidelines, v5.0. The items that are not stipulated in the NCI-CTCAE, v5.0 will be assessed according to the criteria below and entered into the eCRF:

Table 11 Grading Scale Defining the Severity of an Adverse Event

Grade	Assessment Standard
1 - Mild	Asymptomatic or mild symptoms, clinical or diagnostic observations only; intervention not indicated
2 - Moderate	Minimal local or noninvasive intervention indicated; limiting age-appropriate instrumental ADL†
3 - Severe	Medically significant but not immediately life threatening, hospitalization or prolonged hospitalization indicated; disabling; limiting self-care ADL‡
4 - Life-threatening	Life threatening consequences, urgent intervention indicated
5 - Death	Death related to AE

ADL: activities of daily living; AE: adverse event

†Instrumental ADL refer to preparing meals, shopping for groceries or clothes, using the telephone, managing money, etc.

‡Self-care ADL refer to bathing, dressing and undressing, feeding self, using the toilet, taking medications and not bedridden.

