### **5.2.3 Safety Endpoint: Adverse Events (AEs)**

An AE is any untoward medical occurrence in a participant or clinical study participant, temporally associated with the use of study IP and other study treatments, whether or not considered related to the study IP and other study treatments.

A treatment-emergent adverse event (TEAE) is defined as an AE observed after starting administration of the IP until 30 days after the final administration of IP. An IP-related TEAE is defined as any TEAE with a causal relationship assessed as “yes” by the investigator or with missing assessment of the causal relationship.

If the adverse event occurs on Day 1 and the onset check box is marked “Onset after first dose of study IP” or the onset check box is left blank, then the adverse event will be considered treatment emergent. If the adverse event occurs on Day 1 and the onset check box is marked “Onset before first dose of study IP”, then the adverse event will not be considered treatment emergent. If a participant experiences an event both during the pre-investigational period and during the investigational period, the event will be considered as TEAE only if it has worsened in severity (i.e. it is reported with a new start date). All adverse events

collected that begin within 30 days after taking the last dose of study IP will also be counted as TEAE.

The number and percentage of participants with TEAEs, IP-related TEAEs, serious TEAEs, IP-related serious TEASs, TEAEs leading to withdrawal of treatment and IP-related TEAEs leading to withdrawal of treatment will be summarized by SOC, preferred term and treatment group. The number and percentage of TEAEs by severity will also be summarized. The worst severity will be summarized if the same AE is recorded more than once for a participant.

AE data will be listed.

Immune-related AE (irAE) and infusion related reactions (IRR) will be considered as Adverse Events of Special Interest (AEsi). The list of events classified as AEsi may change during the study due to ongoing pharmacovigilance.

Time to first onset of irAE will follow the following algorithm:

Situation	Date of Event or Censor	Outcome
AE of interest observed	Date of first onset	Event
No AE of interest observed and treatment ongoing	Date of data cutoff	Censor
No AE of interest observed and treatment discontinued	Date of last dose + 30 days	Censor

Time to First Onset = Date of Event or Censor – Date of First Dose +1

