## **6 STATISTICAL METHODOLOGY**

### **6.1 General Considerations**

For continuous variables, descriptive statistics will include the number of participants (n), mean, standard deviation, median, minimum, and maximum. When needed, the use of other percentiles (e.g., 10%, 25%, 75% and 90%) will be reported in the relevant section. In addition, for plasma concentrations and continuous PK parameters, the coefficient of variation (CV) and the geometric mean will also be calculated. Frequencies and percentages will be displayed for categorical data. Percentages by categories will be based on the number of participants with no missing data, i.e., will add up to 100%.

Summaries based on FAS and RAS (e.g., disposition, baseline, and efficacy data) will be presented by planned treatment, unless specifically stated otherwise. Safety analysis and other summaries based on SAF, PKAS or PDAS will be presented by actual dose level received.

Baseline is defined as the last available measurement prior to the first dose of IP.

Unless otherwise specified, all summaries will be presented overall, by dose level, and by phase.

All data processing, summarization, and analyses will be performed using Statistical Analysis Software (SAS)® Version 9.4 or higher on Linux. Specifications for table, figure, and listing (TLF) formats can be found in the TLF specifications for this study.

Study day will be calculated in reference to the first dose date. For assessments conducted before the first dose, study day will be calculated as (assessment date – first dose date). For assessments conducted on or after the first dose, study day will be calculated as (assessment date – first dose date + 1).

For the definition of subgroups of interest, please refer to Section [6.8](#).

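### In the AE tables by CTCAE grade, one ungraded record turns a participant with a known Grade 3–5 event into a missing-grade participant, who then leaves the Grade 3 or higher category

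*SAP*

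**What the plan says.** SAP 6.5.2 plans SOC and PT tables by CTCAE severity grade, with groupings below Grade 3 and Grade 3 or higher. One set covers all TEAEs and one covers IP-related TEAEs. Where a participant has several events in the same SOC or PT, the participant is "counted only once with the worst severity grade and highest degree of relationship". An exception follows: "if any of the severity grade or relationship values are missing then the participant will be counted only once with missing severity grade or relationship". Nothing exempts a participant whose other records already carry a Grade 3, 4 or 5.

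Other provisions bear on this:

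- SAP 5.2.3: "The worst severity will be summarized if the same AE is recorded more than once for a participant". Protocol 9.4.3.1 has the same sentence. Neither gives an exception for missing grades.
- SAP 6.5.2 separately lists "CTCAE Grade 3 or higher TEAEs" among its SOC/PT summaries, plus an IP-related version, and states no missing-grade rule for them.
- SAP 5.2.3 defines an IP-related TEAE as one with causality answered yes "or with missing assessment of the causal relationship".
- SAP 6.1: "Percentages by categories will be based on the number of participants with no missing data, i.e., will add up to 100" per cent.
- Protocol 10.3.4: "AEs, including abnormal clinical laboratory values, will be graded using the NCI-CTCAE guidelines, v5.0". A fallback scale covers events that CTCAE does not list.
- Protocol 7.3.1: when a grade changes, "the event should be relisted on the eCRF with the new NCI-CTCAE grade/grade and new onset date".
- Protocol 9.6 rules out imputation as a general principle. Its stated exceptions are AE and medication dates, so a missing grade stays missing.

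**The concern.** A missing grade on one record cannot make a known Grade 4 on another less severe. Whatever the missing value would have been, the participant's worst grade is at least 4 and the participant belongs in Grade 3 or higher. The exception discards information that already settles the category.

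It can also make planned outputs disagree. If the separate Grade 3 or higher tables select events by their recorded grade, they will count a participant whom the by-grade table shows as missing for the same SOC or PT. With few participants per dose level, one such reclassification visibly changes a row.

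**Working it through.** The plan gives no figure to reproduce, because this is a counting rule. The check applies the rule literally and compares it with a worst-known-grade rule.

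**Step 1. Apply both rules to one participant's records in one SOC or PT row.**

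| Grades recorded | SAP 6.5.2 as written | Worst known grade |
|---|---|---|
| 3 and missing | missing | 3 |
| 4 and missing | missing | 4 |
| 5 and missing | missing | 5 |
| 2 and missing | missing | 2 |
| 3 and 1 | 3 | 3 |
| missing only | missing | missing |

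In the first three rows the written rule removes a participant who is certainly Grade 3 or higher.

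**Step 2. SOC level.** The rule also applies to SOC rows. A Grade 4 event in one PT and an ungraded record in a different PT of the same SOC leave the PT row at Grade 4 but turn the SOC row above it to missing.

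**Step 3. Compare with the other severity rule.** For repeat records of the same AE, SAP 5.2.3 and Protocol 9.4.3.1 call for the worst severity, while 6.5.2 reports missing. For different AEs within one SOC, those two sections are silent, so the departure is limited to repeat records.

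**Step 4. Size in an assumed row.** Take 6 participants, the minimum Protocol 4.1 requires at the dose level used to determine the RP2D. This is not a known final number. Assume grades {3, missing}, {3}, {2}, {1, 2}, and two participants with no event in the row. Under worst known grade, 2 participants are at Grade 3 or higher, 2 are below and none are missing. Under the written rule the counts are 1, 2 and 1.

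The percentage depends on the denominator, which the SAP does not settle for these tables:

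| Denominator | Worst known grade | As written | Fall (points) |
|---|---|---|---|
| All 6 | 2/6 = 33.3% | 1/6 = 16.7% | 16.7 |
| Non-missing (6.1), no-event participants kept | 2/6 = 33.3% | 1/5 = 20.0% | 13.3 |
| Graded participants in the row only | 2/4 = 50.0% | 1/3 = 33.3% | 16.7 |

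On the second denominator, with x of n participants at Grade 3 or higher and one masked, the fall is x/n − (x − 1)/(n − 1) = (n − x)/(n(n − 1)). At n = 6 this is (6 − x)/30: 16.7, 13.3, 10.0, 6.7, 3.3 and 0 points for x = 1 to 6.

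On a fixed denominator one participant is 100/n points: 16.7 at n = 6 and 8.3 at n = 12, the planned phase 1 size.

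**Step 5. Compare the two tables.** If the separate Grade 3 or higher table selects records by grade, it counts 2 participants in this example. The by-grade table counts 1.

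**The case against.** The strongest objection is that the rule may never operate. Protocol 10.3.4 requires every AE to be graded and supplies a fallback scale, and relisting under 7.3.1 adds records that carry the new grade. No passage suggests that grades will be missing. This stands as a limit on frequency. It does not justify the clause, which exists only for the case where a grade is missing and gives the wrong category there when another record is Grade 3 or higher.

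A second objection is that 5.2.3 and Protocol 9.4.3.1 are general and do not mention missing grades, so the more specific clause in 6.5.2 may be read as completing them. For Grade 1 or 2 plus an ungraded record this has force: the true worst grade is unknown, and showing missing avoids implying that it was below 3. The argument fails where the known grade is 3 or higher, because the category is then certain. The flag proposed below covers the lower-grade case.

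Third, the mismatch with the Grade 3 or higher tables depends on how those tables select events, which the SAP does not say. That is correct, and the mismatch is stated only conditionally. The percentages are likewise illustrative. In particular, keeping no-event participants in the denominator sits awkwardly with the 6.1 requirement that categories total 100 per cent.

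Finally, the consequences are limited. The event remains in the SOC/PT totals, the AE listing and any applicable death table. Dose escalation under Protocol 4.1 uses DLT counts, and no passage makes this table an input to a dose decision. This stands and sets the severity.

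**Conclusion.** The rule is wrong as written, at minor severity. When a participant has a known Grade 3–5 record and an ungraded record in the same row, the by-grade table drops that participant from Grade 3 or higher, lowering that count by one. That follows from the text alone.

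The percentage effect rests on an assumed row size and denominator. How often it occurs cannot be estimated because the documents give no missing-grade rate, and the effect is nil if every record is graded. It does not touch dose escalation, the listings or the total event counts.

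**What to change.** Replace the exception in SAP 6.5.2 with wording such as:

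*The participant is counted once at the worst non-missing grade. Missing grade is shown only when all of the participant's records for that SOC or PT lack a grade. A missing relationship is handled as in Section 5.2.3.*

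The last sentence aligns the table with the definition in 5.2.3, which already counts missing causality as IP-related. No grade is imputed, so Protocol 9.6 is respected.

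Also flag every participant who has any ungraded record, in the AE listing or a table footnote. Otherwise a participant with a Grade 1 record and an ungraded one would look fully graded.

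The cost is one SAP sentence and a small programming change. A listing flag is the cheapest form; a footnote for each table row costs more. SAP Section 1 provides for approval before database lock and for documenting changes that affect the analyses in the clinical study report, so there is a route for the change.

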#### **6.5.3 Adverse Events of Special Interest (AEsi)**

The number and percentage of participants with Adverse Events of Special Interest (AEsi) such as IRR, irAE, and as classified by SOC and PT, will be summarized by dose level, phase, and overall.

#### **6.5.4 Clinical Laboratory Evaluation**

The baseline visit is the last measurement taken prior to initial study IP administration.

Quantitative clinical laboratory variables, i.e., hematology, biochemistry, coagulation and urinalysis will be summarized using mean, standard deviation, minimum, maximum and median by phase and dose level at each visit. Additionally, a within-participant change will be calculated as the post-baseline measurement minus the baseline measurement and summarized in the same way.

The number and percentage of participants in relevant categories will be summarized for each dose level, phase, and overall at each visit.

Frequency tabulations of qualitative clinical laboratory variables (urinalysis) will be presented by dose level, phase, and overall at each visit.

Laboratory results will also be graded using NCI-CTCAE, where possible. NCI-CTCAE grade of laboratory evaluations will be summarized by number and percentage of participants for each visit. Shift tables of NCI-CTCAE grade change from baseline to worst post-baseline grade will also be presented.

Laboratory results will be listed.

#### **6.5.4.1 Liver Safety Assessment**

The following potentially clinically significant criteria in liver function tests for Alkaline Phosphatase (ALP), Alanine Transaminase (ALT), total bilirubin (TBL), Aspartate Transaminase (AST) and their combination are defined. The participant's highest value during the investigational period will be used.

Parameter	Criteria
ALT	> 3xULN > 5xULN > 10xULN > 20xULN
AST	> 3xULN > 5xULN > 10xULN > 20xULN
ALT or AST	> 3xULN > 5xULN > 10xULN > 20xULN
TBL	> 2xULN
ALP	> 1.5xULN
ALT and/or AST AND TBL (*)	(ALT and/or AST > 3xULN) and (TBL > 2xULN)
ALT and/or AST AND TBL AND ALP (*)	(ALT and/or AST > 3xULN) and TBL > 2xULN and ALP < 2xULN

ALT: alanine aminotransferase; ALP: alkaline phosphatase; AST: aspartate aminotransferase; TBL: total bilirubin; ULN: upper limit of normal

(\*) Combination of values measured within same sample

The number and percentage of participants with potentially clinically significant values in liver enzymes and total bilirubin during the investigational period will be presented by dose level, phase, and overall.

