A DLT is defined as any of the following events that occur within 28 days starting with the first dose on C1D1 in the dose escalation cohort and that is considered to be possibly, probably or definitely related to IP. Confirmation of DLTs will be made by the DESC. The severity of AEs will be assessed according to National Cancer Institute's Common Terminology Criteria for Adverse Events (NCI-CTCAE), v5.0. Participants experiencing DLTs, who in the opinion of the investigator are deriving clinical benefit from the study treatment (e.g., marked reduction in tumor burden), may be allowed to continue study treatment with ASP0739 upon resolution of the event to \leq grade 1 or baseline, upon discussion with the sponsor. Participants experiencing DLTs during the single agent dose escalation phase will not be replaced.

DLTs are defined as follows:

- Grade \geq 2 autoimmune reaction
- Grade 3 irAEs that do not resolve to grade \leq 1 in 3 to 5 days
- Grade 4 irAEs
- Grade \geq 3 non-hematological AE that does not resolve to grade \leq 2 within 72 hours of onset
- Grade 4 neutropenia
- Grade 3 febrile neutropenia with or without infection
- Grade 4 thrombocytopenia
- Grade 3 thrombocytopenia accompanied by bleeding that requires any transfusion
- Grade 4 anemia
- Grade 3 anemia requiring transfusion
- AST or ALT $> 5 \times$ upper limit of normal (ULN; grade \geq 3) without liver metastases
- AST or ALT $> 8 \times$ ULN in participants with liver metastases
- AST or ALT $> 3 \times$ ULN and total bilirubin (TBL) $> 2 \times$ ULN (in participants with Gilbert syndrome: AST or ALT $> 3 \times$ ULN and direct bilirubin > 1.5) (confirmed Hy's Law)
- Grade \geq 3 liver function test abnormality lasting \geq 7 days

- Grade 5 toxicity
- Prolonged delay (> 2 weeks) in initiating cycle 2 due to treatment-related toxicity

The following AEs will not be considered DLTs:

- Electrolyte abnormalities that are not associated with clinical sequelae or deemed not clinically significant and corrected with appropriate management or supplementation within 72 hours of onset
- Grade 3 infusion site reaction if successfully managed and resolved within 72 hours of onset
- Alopecia, anorexia or fatigue

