5. Participant consents to provide an archival tumor specimen in a tissue block or unstained serial slides prior to IP administration. If an archival tissue sample is not available, enrollment into the study should be discussed with the medical monitor.
6. Participant in phase 2 consents to provide tumor specimen obtained within 56 days prior to first dose of study treatment, as tissue block or unstained serial slides. If a recent tissue sample cannot be provided due to medical or safety concerns, enrollment into the study must be discussed with the medical monitor.
7. Participant in phase 2 consents to undergoing a tumor biopsy (core needle biopsy or excision) during the treatment period as indicated in the schedule of assessments.
8. Participant has an Eastern Cooperative Oncology Group (ECOG) performance status of ≤ 2 .
9. Participant with life expectancy of ≥ 12 weeks at the time of screening.
10. Participant must meet the following criteria as indicated on the clinical laboratory tests during screening period:
 - Serum AST and ALT $\leq 2.5 \times$ ULN (or $< 5 \times$ ULN if known liver metastases)
 - Serum TBL $\leq 1.5 \times$ ULN (or $< 3 \times$ ULN if known liver metastases)
 - Serum creatinine $\leq 1.5 \times$ ULN or an estimated glomerular filtration rate of > 50 mL/min as calculated by the Modification of Diet in Renal Disease equation.
 - Platelets $\geq 100000/\mu\text{L}$
 - ANC $\geq 1500/\mu\text{L}$
 - Hemoglobin $\geq 9 \text{ g/dL}$
 - Prothrombin time/international normalized ratio (PT/INR) $< 1.5 \times$ ULN unless on warfarin.
 - PTT $< 1.5 \times$ institutional normal limits.
11. A female participant is eligible to participate if she is not pregnant [Section 10.2 Appendix 2: Contraception Requirements] and at least one of the following conditions apply:
 - Not a woman of childbearing potential (WOCBP) as defined in [Section 10.2 Appendix 2: Contraception Requirements]
 - OR

- WOCBP who agrees to follow the contraceptive guidance as defined in [Section 10.2 Appendix 2: Contraception Requirements] throughout the treatment period and for at least 6 months after the final IP administration.
- 12. Female participant must not be breastfeeding at screening or during the study period and for 6 months after the final IP administration.
- 13. Female participant must not donate ova at screening and throughout the study period and for 6 months after the final IP administration.

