10.4 Appendix 4: Liver Safety Monitoring and Assessment

The purpose of this appendix is to provide guidance for the monitoring of drug-induced liver injury during the course of the study. It should be noted that this section does not specify the end-of-study analyses of liver enzymes. The end-of-study liver enzymes analyses will be described in the SAP. Any participant enrolled in a study with active drug therapy and reveals an increase of serum aminotransferases (AT) to $> 3 \times$ ULN or bilirubin $> 2 \times$ ULN should undergo detailed testing for liver enzymes (including at least alkaline phosphatase [ALP], ALT, AST and TBL). Testing should be repeated within 72 hours of notification of the test results. For studies for which a central laboratory is used, alerts will be generated by the central laboratory regarding moderate and severe liver abnormality to inform the investigator and study team. Participants should be asked if they have any symptoms suggestive of hepatobiliary dysfunction.

Definition of Liver Abnormalities

Confirmed abnormalities will be characterized as moderate and severe where ULN is as shown below.

Table 12 Moderate and Severe Liver Abnormalities

	ALT or AST		TBL
Moderate	$> 3 \times$ ULN	or	$> 2 \times$ ULN
Severe	$> 3 \times$ ULN	and†	$> 2 \times$ ULN

ALT: alanine aminotransferase; AST: aspartate aminotransferase; TBL: total bilirubin; ULN: upper limit of normal

†Samples taken simultaneously or within maximum 24 hours.

In addition, the participant should be considered to have severe hepatic abnormalities for any of the following:

- ALT or AST $> 8 \times$ ULN
- ALT or AST $> 5 \times$ ULN for more than 2 weeks.
- ALT or AST $> 3 \times$ ULN and† TBL $> 2 \times$ ULN or international normalized ratio (INR) > 1.5 (if INR testing is applicable/evaluated)
- ALT or AST $> 5 \times$ ULN and† (TBL $> 2 \times$ ULN in participants with liver metastases)
- ALT or AST $> 3 \times$ ULN with the appearance of fatigue, nausea, vomiting, right upper quadrant pain or tenderness, fever, rash and/or eosinophilia ($> 5\%$)

† Samples taken simultaneously or within a maximum of 24 hours.

The investigator may determine that abnormal liver function results, other than as described above, may qualify as moderate or severe abnormalities and require additional monitoring and follow-up.

Follow-up Procedures

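### The combined ALT/AST and bilirubin row in SAP 6.5.4.1 has no baseline reference, so a participant with liver metastases can meet it on entry values and be counted without any change

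*SAP*

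**What the plan says.** **Entry limits (Protocol 5.1, criterion 10).** For transaminases: "Serum AST and ALT $\leq 2.5 \times$ ULN (or $< 5 \times$ ULN if known liver metastases". For bilirubin: "Serum TBL $\leq 1.5 \times$ ULN (or $< 3 \times$ ULN if known liver metastases".

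**SAP liver table (6.5.4.1).** The table counts participants who exceed fixed multiples of ULN. The combined row is ("ALT and/or AST > 3xULN) and (TBL > 2xULN"), both in the same sample. A further row adds ALP below 2×ULN. On which value enters, the SAP says that the participant's "highest value during the investigational period will be used". No row has a condition on baseline, liver metastases or cause.

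**Other laboratory output (SAP 6.5.4).** Change from baseline is summarized by visit, and "Shift tables of NCI-CTCAE grade change from baseline to worst post-baseline grade will also be presented". Results are also listed.

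**Protocol monitoring and DLT lines.** Appendix 4 (10.4) classes AST/ALT above 3×ULN with TBL above 2×ULN as severe for everyone, both in Table 12 and in the list below it. It then adds a line for AST/ALT above 5×ULN with TBL above 2×"ULN in participants with liver metastases". The same two lines return in its list on stopping study treatment. The DLT lists in 4.1 separate participants with and without liver metastases for AST/ALT alone. In the combined AST/ALT and TBL line they make an exception only for Gilbert syndrome.

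**The concern.** Protocol 2.3.1.1 names the liver as a target organ of toxicity, so readers of the safety tables will look at this one. If the combined row can be met on entry values alone, its count mixes abnormality that was there before dosing with change after dosing, and a reader cannot separate the two. The harm runs both ways: stable pre-existing elevation looks like a finding, and genuine worsening in a participant who entered high adds nothing to the row.

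The SAP handles other safety measures differently. In 6.5.5, SBP, DBP and pulse rate need both an absolute threshold and a change from baseline, and the highest post-baseline value is specified. In 6.5.6, QTcF has separate change-from-baseline categories. In the protocol, Table 16 footnotes a to c switch to multiples of baseline when baseline is abnormal.

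**Working it through.** No sample size or error rate is involved. The check is whether the entry limits overlap each liver line. AT stands for AST or ALT; all values are multiples of ULN.

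| Line | Condition | Source |
|---|---|---|
| Entry, liver metastases | AT < 5, TBL < 3 | Protocol 5.1, criterion 10 |
| Entry, no liver metastases | AT ≤ 2.5, TBL ≤ 1.5 | Protocol 5.1, criterion 10 |
| SAP combined row | AT > 3 and TBL > 2, same sample | SAP 6.5.4.1 |
| Appendix 4 general severe line | AT > 3 and TBL > 2 | Protocol 10.4, Table 12 and list |
| Appendix 4 liver-metastasis line | AT > 5 and TBL > 2 | Protocol 10.4 |
| DLT combined line | AT > 3 and TBL > 2 | Protocol 4.1 |
| DLT AT-alone line, liver metastases | AT > 8 | Protocol 4.1 |
| DLT TBL-alone line, combination only | TBL > 3 | Protocol 4.1 |

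**Step 1: overlap with the SAP row.** With liver metastases, {AT < 5, TBL < 3} and {AT > 3, TBL > 2} intersect in 3 < AT < 5 with 2 < TBL < 3. On a grid of 0.1×ULN this is 19 AT values (3.1 to 4.9) by 9 TBL values (2.1 to 2.9), or 19 × 9 = 171 eligible points. Without liver metastases the entry maxima are 2.5 and 1.5, both below the row's thresholds, so the overlap is empty. The row that adds ALP is also met at entry if ALP is below 2.

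**Step 2: what the row then shows.** Take two eligible participants entering at AT 4 and TBL 2.5. One stays there; the other rises to AT 9 and TBL 5. Each adds exactly 1 to the combined row. The second also reaches the >5×ULN AT row, but TBL has only one row (>2×ULN), which both had passed before dosing.

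**Step 3: whether other output fills the gap.** The shift tables and changes from baseline treat ALT, AST and TBL separately. None shows whether the same-sample combination was present at baseline.

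**Step 4: size.** One participant counted on unchanged values contributes 1/3 = 33% of a dose level of 3, 1/4 = 25% of 4, or 1/6 = 17% of 6. How many participants enter in this band is not stated.

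**Step 5: the protocol lines.** Any value with AT > 5 and TBL > 2 also has AT > 3 and TBL > 2, so the Appendix 4 liver-metastasis line lies wholly inside the general line and changes no classification. No eligible entry value meets that line, the DLT AT > 8 line, or the combination TBL > 3 line, since entry requires TBL strictly below 3. The only DLT threshold that entry values can exceed is the combined one.

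**The case against.** The SAP calls these rows potentially clinically significant values, which makes the table a numeric screen. It never labels anyone a Hy's Law case. A reader might infer that the table will produce false Hy's Law cases, because the DLT list attaches that name to the same thresholds. The documents do not support that. Protocol 10.3.1.2 limits potential cases to those without other causes of liver injury, and Appendix 4 excludes pre-existing liver disease. Nor will everyone who enters in the band be counted: values may fall after dosing, and some participants may truly worsen.

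A reader might also infer that an unchanged entry value is a DLT and could move a cohort from 0/3 to 1/3. That does not follow. Protocol 4.1 requires an event within 28 days of first dose, related to treatment and confirmed by the DESC.

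Appendix 4 is guarded as well. It disclaims the end-of-study analysis, and its SAE-reporting and discontinuation text allows for another explanation. The study ended early without combination treatment (SAP 1), and with few participants the listings show each course. The CTCAE shift tables may themselves reflect baseline multiples, though the SAP does not say so.

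All this narrows the point. None of it reaches the combined row, which applies no filter for cause, metastases or baseline.

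**Conclusion.** The point holds for the combined row of SAP 6.5.4.1 and for participants with known liver metastases only. Entry values with AST/ALT above 3 and below 5×ULN and TBL above 2 and below 3×ULN already exceed it, so the row cannot distinguish stable entry abnormality from new or worsening injury. With one such participant the reported proportion could rest on 33%, 25% or 17% of a dose level of 3, 4 or 6. This assumes that at least one participant enters in the band and stays above both thresholds in one post-dose sample; the documents give no frequency. It also treats the screening value as the baseline, although the SAP takes the last measurement before first dose.

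The protocol part is one of consistency: a liver-metastasis line in Appendix 4 that has no effect, and a DLT list that allows for liver metastases in AST/ALT alone but not in the combined line. It does not show that any dose decision was or would be affected.

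**What to change.** **SAP 6.5.4.1.** Keep the existing row and state that post-baseline values are used. Split or flag its counts by whether the participant met the criterion at baseline. Add a baseline-referenced version: a shift of the combined criterion from baseline to worst post-baseline, or multiples of baseline when baseline is abnormal, in the manner of Table 16 footnotes a to c. Show the table by liver metastases if that is recorded; the planned baseline and disease-history summaries (SAP 6.2.3 and 6.2.4) do not name it.

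Baseline-positive participants should not simply be dropped. Someone who starts at 3.1 and 2.1×ULN and rises to 15 and 8×ULN would then vanish from the count.

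**Protocol.** Criterion 10, the combined and AST/ALT-alone DLT lines in 4.1, and the general and liver-metastasis lines in Appendix 4 (including its list on stopping treatment) must be reconciled. Which thresholds should apply is a clinical decision and is not proposed here.

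**Cost.** One extra split of a planned table, with smaller cells, using laboratory values already collected. The liver-metastasis display depends on that status being available. The protocol part is an alignment of text.
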